4. STUDY DESIGN AND POPULATION

4.1. Overview of study design

In this phase IIb, double-blind, cross-over placebo-controlled trial, we will assign 84 subjects with HFpEF to: (A) Potassium nitrate administered by mouth at a dose of 6 mEq three times daily for approximately 6 weeks, or (B) Potassium chloride (KCI) at identical doses. The order of the interventions (AB-BA design) will be randomized, with a 1-week washout period separating each

intervention. A crossover design will enable each subject to receive both treatments, reducing inter-individual variability and maximizing our power to detect effects of potassium nitrate vs. placebo (KCl). The active drug (KNO₃-) and control (KCl) will be prepared at the Investigational Drug Pharmacy at the University of Pennsylvania and dispensed by an investigational drug pharmacist, blinded to both the subjects and the investigators.

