Subjects that qualify for a 3T or 7T scanner (for the leg MRI study) also qualify for scanning in a 1.5T scanner (for the cardiac MRI substudy). However, the opposite is not necessarily true. Subjects who are determined eligible to undergo scanning in a 3T or 7T scanner (in the primary study) are eligible to undergo scanning in the 1.5T scanner (for the cardiac MRI study). Some situations (such as many intraluminal stents and prosthetic valves) which would exclude scanning at high field (7T or 3T) are considered safe for 1.5T scanning. Subjects who are deemed ineligible to undergo 7T or 3T scanning in the parent trial, may still be enrolled in the ancillary myocardial perfusion study and undergo a cardiac MRI study (at 1.5T). In all cases, participation in the myocardial perfusion / cardiac MRI ancillary study will be approved by [name], who has appropriate clinical expertise to assess the safety of this test, according to current clinical standards. [name] is the Director of Advanced Cardiac Imaging at the CMJC Philadelphia VA Medical Center and Assistant Professor at the University of Pennsylvania.

4.3.3. Criteria that will prompt exclusion from the trial at the 6 week visit

Subjects will be discontinued from study participation if they meet any of the following criteria at the 6-week study visit:

- 1. Acute coronary syndrome or coronary intervention for unstable coronary disease after enrollment
- New onset ischemia on stress testing since the time of enrollment, including clinically significant reversible ischemia in a coronary distribution identified during the cardiac MRI substudy.
- 3. New treatment with organic nitrates or phosphodiesterase inhibitors that cannot be withheld
- 4. Serum K>5.5 mEq/L
- 5. Any medical condition that, in the opinion of the investigator, will interfere with the safe completion of the study, or the validity of endpoint assessments. Although the ultimate authority/decision making will rely on each site PI, these ad-hoc discontinuations will be discussed with the other site PIs, the chair of the trial and the medical director of the IND for input.

Subjects who meet the criteria below will not be immediately discontinued, but will be scheduled for an ad hoc additional visit for reassessment of values prior to drug initiation in phase 2:

- 1. Supine systolic blood pressure <90 mm Hg
- 2. Acute kidney injury with eGFR < 30 mL/min/1.73m2
- 3. Methemoglobinemia baseline methemoglobin level >5%

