If these criteria persist during the ad-hoc visit, the subject will be discontinued from the study.

4.3.4 Conditions that will preclude participation in the myocardial perfusion ancillary study include:

- 1. Prior allergic reactions to gadolinium-based contrast agents.
- 2. Allergy, or prior severe adverse reactions to regadenoson or aminophylline.
- 3. 2nd degree AV block, 3rd degree AV block or high-grade AV block.

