- Data download of the Aurora device and Actigraph

Additional visit for subjects participating in the Cardiac MRI sub-study: Subjects who participate in the MPR ancillary study will undergo a cardiac MRI with regadenoson administration. This will be scheduled during the last 2 weeks of the study intervention (4-6 weeks after initiation of drug administration in Phase 1), such that it will not interfere with the scheduling of the main trial visits. The cardiac MRI may take place on a different day than the exercise study or the lower extremity MRI scan and may occur either before or after the exercise endpoint study visit.

5.4. 1-week washout period

Following the endpoint assessment, subjects will enter a 1-week washout period during which they will not receive any study medications.

5.5. Intervention Phase 2

Following the washout period, subjects will receive either active drug (KNO₃) or placebo (KCI) during phase 2 of the trial. Subjects will receive the intervention (KNO₃ or KCI) that was not administered in phase 1, such that each subject will receive both study interventions in this cross-over design. The ~1-week call and the ~6-week study visit will be repeated as above. We will provide subjects with a 14-day supply of study medication to account for potential delays in the shipment of the 2nd batch of medication (i.e., after the 1-week call).

1-week call: Subjects will be called by telephone ~1 week later for side-effect assessment. Subjects will receive reinforcement of the dietary restrictions imposed during the study. Subjects will be asked about headaches and dizziness. If these symptoms are not present, or are not different than the subject's baseline, the drug dose will be up-titrated to 18 mmol daily (One 6mmol capsule taken 3 times per day). The presence of orthostatic symptoms will prompt a visit to assess for orthostatic vital signs. The presence of symptomatic orthostatic hypotension (20 mmHg reduction in systolic blood pressure with associated symptoms such as dizziness) will prompt exclusion of patients from the trial.

Subjects may experience symptoms upon dose uptitration that do not prompt exclusion from the trial, as per the criteria noted above (for example, but not limited to, mild dizziness, gastrointestinal

symptoms, fatigue). In these instances, the Site Principal Investigator can reduce the dose back to 6-mmol capsule taken twice per day, for the remainder of the treatment phase.

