Safety Clinical Laboratory Tests: Laboratory evaluations will be collected prior to study drug initiation. Among women who are not surgically sterilized or post-menopausal, a urine pregnancy test will be performed at screening (prior to all baseline studies and drug initiation), at the end of the first treatment phase (prior to the MRI study and initiation of the second treatment phase) and immediately before the MRI study performed at the end of the second treatment phase. Methemoglobin levels will be measured before initiation of randomized therapy and approximately 6 weeks after initiation of randomized therapy in both treatment phases (1 and 2). Methemoglobinemia (methemoglobin levels >10%) will prompt discontinuation of patients from the trial. Other tests, including a complete blood count, liver enzymes, a basic metabolic panel (including serum creatinine for assessments of renal function) will also be performed prior to randomization and approximately 6 weeks after initiation of randomized therapy.

Significant methemoglobinemia was not observed in our pharmacokinetics trial, at the same doses used in this trial, in the same patient population. In this study we measured methemoglobin every half hour after the first administration as well as during steady-state continued oral administration at doses of both 12 mmol/d and 18 mmol/d (same dosing scheme used in the KNO₃CK OUT HFpEFp trial).

Side Effect Management Plan: No side effects have been observed in our single-dose study or our ongoing pharmacokinetics study (in particular, no hypotension or methemoglobinemia). However, a plan for management of side effects will be in place. The use of acetaminophen may be used for headaches during the study. Although hypotension is not expected, it should be managed as per standard clinical practice. In the unlikely event that methemoglobinemia does occur during the trial, we will manage according to best clinical standards.¹⁹⁸ As the endogenous rate of reconversion from methemoglobin to hemoglobin is approximately 15% per hour, most asymptomatic patients can be managed conservatively. Generally, methemoglobin levels >20% with symptoms, or > 30% without symptoms, warrant therapy; any patient with levels that are elevated to this range will be referred to the emergency room for management.¹⁹⁸

11.3.5 Measures to minimize the risk of breach in confidentiality:

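### A first methemoglobin value above 10% at the Phase 1 6-week visit is to be rechecked under 4.3.3 but discontinued under 11.3.4

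*Combined protocol and SAP*

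**What the plan says.** **Methemoglobin.** Section 11.3.4 sets the schedule: "Methemoglobin levels will be measured before initiation of randomized therapy and approximately 6 weeks after initiation of randomized therapy in both treatment phases". It then gives the stopping rule: "Methemoglobinemia (methemoglobin levels >10%) will prompt discontinuation of patients from the trial". It mentions no repeat test.

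Section 4.3.3 lists the criteria applied at the 6-week visit. One group leads to discontinuation. A second group is handled differently: "Subjects who meet the criteria below will not be immediately discontinued, but will be scheduled for an ad hoc additional visit", before Phase 2 drug is started. The third item in that second group is "Methemoglobinemia baseline methemoglobin level >5" per cent, and the list closes with: "If these criteria persist during the ad-hoc visit, the subject will be discontinued from the study". Item 5 of the first group lets the investigator stop a subject for a medical condition that "will interfere with the safe completion of the study, or the validity of endpoint assessments", after discussion with the other site PIs, the chair and the medical director.

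Under Section 5.5 the subject next receives the treatment "that was not administered in phase 1, such that each subject will receive both study interventions in this cross-over design". Section 4.1 describes the treatments as dispensed "blinded to both the subjects and the investigators".

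**SAE capture.** Section 7.3 captures SAEs from consent to a Week 15 phone visit. Section 5.5 ends participation at the Phase 2 6-week visit. Section 5.7 gives subjects who stop early an early termination visit and nothing after it.

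**Smaller items.** Section 7.2 names dipyridamole for reversing regadenoson, whereas 8.9 uses intravenous aminophylline and 4.3.4 excludes for reactions to aminophylline. Section 11.3.4 enrolls at supine SBP above 110, whereas 4.3.2 excludes below 100. Section 11.3.7 calls eGFR above 30 an exclusion, the reverse of criterion 19 in 4.3.2.

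**The concern.** Site staff who see a first methemoglobin value above 10% at the Phase 1 6-week visit can find two instructions and no statement of which prevails. One keeps the subject in pending a recheck; the other ends participation.

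What is at stake depends on sequence. A KNO3-first subject goes on to KCl, so staying in adds no study nitrate, and a hard stop costs only the Phase 2 value. A KCl-first subject goes on to KNO3, so following 4.3.3 can lead to nitrate exposure that 11.3.4 would have prevented. The next scheduled methemoglobin test is then about 6 weeks into Phase 2. Because the investigator is blinded, one rule has to serve both cases.

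For SAEs, the window in 7.3 is longer than the follow-up that Section 5 describes, so no described contact would collect new events in the last part of it.

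**Working it through.** **1. The two methemoglobin rules side by side, Phase 1 6-week visit, first value**

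| First value | 4.3.3 | 11.3.4 | Conflict? |
|---|---|---|---|
| 5% or below | no action | no action | no |
| above 5% to 10% | recheck, stop if it persists | no action | no; 4.3.3 works as a lower tier |
| above 10% | recheck, stop if it persists | stop | yes |

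The 4.3.3 item also says baseline although the visit is on treatment. Its wording matches exclusion 21 in 4.3.2, which suggests carried-over text.

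**2. Where the 11.3.4 rule can act.** The scheduled tests are before therapy and at the two 6-week visits. Before therapy, 4.3.2 already excludes above 5%. The Phase 2 6-week visit is the last one. So among scheduled tests, the Phase 1 6-week visit is the only one at which 11.3.4 can change what a subject receives, and it is the one where 4.3.3 says something else.

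**3. Do the rules differ in outcome?** Input: reconversion of about 15% per hour (11.3.4). Assumptions: first-order decline, no new methemoglobin formed. Level after t hours = start × 0.85^t, so the time to reach 5% is ln(5/start) / ln(0.85).
- From 10%: ln(0.5)/ln(0.85) = 4.3 hours.
- From 20%: ln(0.25)/ln(0.85) = 8.5 hours.
- From 10%, after 24 hours: 10 × 0.85^24 = 0.2%.

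Residual nitrate (half-life about 6 to 8 hours, Section 3.1) would slow this, but the washout lasts a week. A recheck days later would usually be below 5%: the subject continues under 4.3.3 and is out under 11.3.4. In a KCl-first subject the cause lies outside study nitrate. If that cause persists, the recheck should find it and both rules stop the subject; if it has resolved, the rules diverge.

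**4. Statistical cost of a hard stop.** Expected pairs: 84 × 0.90 = 75.6, taken as 75. One lost pair is 1/75 = 1.3%, and the standard error rises by a factor of √(75/74) = 1.0067, or 0.7%.

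**5. SAE window.** Assumptions: Week 15 counts from Phase 1 drug start, which the plan does not state; washout of exactly 1 week; ±1 week at each 6-week visit (Section 6).
- Final visit: 5 + 1 + 5 = 11, 6 + 1 + 6 = 13, 7 + 1 + 7 = 15 weeks.
- Completers, gap to Week 15: 4, 2 and 0 weeks.
- Subject stopped at the Phase 1 6-week visit, with the termination visit at about that time: 15 − 5 = 10, 15 − 6 = 9, 15 − 7 = 8 weeks.

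**The case against.** **The sections can be read as tiers**, with a recheck above 5% and a stop above 10%. That is a sensible reading and probably the intended one, but neither section states it or refers to the other, and 4.3.3 has no upper limit.

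**Section 4.3.3 is specific to this visit and could be taken to prevail.** This has some force, and it is the reasoning by which the SBP sentence in 11.3.4 is treated here as clerical. The cases differ in part: 4.3 says outright that its criteria decide eligibility, whereas the plan gives no order of precedence for on-study stopping. If 4.3.3 did prevail, 11.3.4 would have no effect on treatment at the only scheduled test where it could have one, so the text would still need amending.

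**Safeguards exist.** Item 5 of 4.3.3 allows an immediate stop and requires discussion across sites. Section 5.7 allows withdrawal for safety. Section 6.1 treats suspected drug-related events as if the subject were on KNO3 and provides emergency unblinding. These stand, and a reader who infers that sites are left to act alone would go too far. None of them makes a stop mandatory above 10%.

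**The harm path is thin.** It needs a value above 10% on a capsule without nitrate, followed by a recheck at or below 5%, which meets the entry threshold again. Section 11.3.4 itself reserves treatment for levels above 20% with symptoms or above 30% without. A reader might infer that the KCl-first half of the sample, about 42 of 84, is at risk; that is a denominator, not an estimate of cases. The pharmacokinetic study at these doses found no clinically significant elevation.

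**On SAEs**, 7.3 shows that the call is intended, Figure 4 is not shown, and the Appendix 1 grid is broken in the text available. It cannot be claimed that the call appears nowhere in the plan, only that Section 5 does not describe it. Section 7.4 follows events already recorded, and with nitrate's short half-life most of a long tail falls well after exposure.

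**Conclusion.** The conflict holds for one situation: a first methemoglobin value above 10% at the Phase 1 6-week visit. It should be fixed because it sits in a safety stopping rule, the two actions can lead to opposite outcomes, and one of them can put a KCl-first subject on KNO3.

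Its size is small. Cases should be very rare, each hard stop costs one pair in about 75, and alpha, estimand and power are unaffected to any practical extent. That the rules diverge in practice rests on the plan's reconversion rate, first-order decline and a recheck off drug.

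The SAE mismatch is secondary. On the text, capture runs to a call that Section 5 does not describe and that follows the stated end of participation. The gap is nominally 2 weeks for completers (0 to 4) and about 9 weeks (8 to 10) for a subject stopped at the Phase 1 visit, if Week 15 counts from Phase 1 drug start.

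The reversal-agent, SBP and eGFR items are drafting slips. A reader might infer from 7.2 that dipyridamole would be given to reverse regadenoson; the procedure in 8.9 and the exclusion in 4.3.4 both name aminophylline, so the documents do not support that.

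**What to change.** In 4.3.3, replace the methemoglobin item with: *above 5% to 10%, recheck before Phase 2 drug and discontinue if still above 5%; above 10%, discontinue*. Drop the word baseline there, and have 11.3.4 refer to 4.3.3 instead of stating its own rule for this visit. The cost is one Phase 2 observation per case, including KNO3-first subjects, for whom the stop avoids no nitrate exposure.

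For SAEs, either add the Week 15 call to 5.5 and to 5.7 for subjects who stop early, with its start point defined and the schedule of events in agreement (one call per subject, at most 84), or end capture at the final or early termination visit and accept the loss of later events.

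Clerical: in 7.2, name aminophylline; in 11.3.4, bring the SBP sentence into line with 4.3.2; in 11.3.7, change the exclusion to eGFR below 30. All of this fits in one wording amendment.

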12. REGULATORY STANDARDS

12.1. Informed consent

The site investigator, or a person designated by the site investigator, will fully inform the subject of all pertinent aspects of the clinical trial including the review of the informed consent form approved by an Institutional Review Board (IRB). Prior to a subject's participation in the clinical trial, the Informed Consent Form will be signed and personally dated by the subject or by the subject's legally acceptable representative. Informed consent may be obtained in-person or virtually. All subjects will receive a copy of the informed consent form.

12.2. Institutional Review Board (IRB)

The site Principal Investigator will submit this protocol to the appropriate IRBs, and will forward to the NHLBI a copy of the written and dated approval by the IRB Chairman and committee. The study (study number, protocol title and version number), the document reviewed (protocol, Informed Consent Form, etc.) and the date of the review will be clearly stated on the written IRB approval opinion. During the study, any amendment or modification to the protocol will be sent to the IRB. It will also be informed of any event likely to affect the safety of subjects or the continued conduct of the study, in particular any change in safety and all updates to the protocol will be sent to IRB.

12.3. Investigational New Drug (IND) application

This trial will be done under our currently open Food and Drug Administration IND (IND#123785) to study this particular drug and preparation in this particular patient population. The IND Sponsor will be responsible for interactions with the FDA, with support from the Sponsor Support Unit within the Office of Clinical Research at the Perelman School of Medicine, University of Pennsylvania.

12.4. Source document handling and archiving

Hard copies of subject's study records, including signed informed consent forms, HIPPA forms, source documents, and other study related materials will be stored in the subject binders, in a locked file cabinet in the research coordinator's study office until archived. Research records will be retained for at least 2 years after the completion of this study. All study electronic files will be kept for at least 6 years after IRB acknowledgement of study termination. Files are not be destroyed or deleted without Sponsor approval. Data will be made available to the study sponsor National Institute of Health (NIH) members of the Institutional Review Board, and the Food and Drug administration, if requested by any of these entities.

13. DATA AND SAFETY MONITORING PLAN:

A data and safety monitoring plan is in place for this study.

15. APPENDIX 1. SCHEDULE OF EVENTS

	Baseline	Phas		1-week	Phase	2
SCHEDULE OF EVENTS	assessment		wee		1	we
		k 6	week	washout	к 6	wee
nformed Consent ^a	x	-	Week		-	
Eligibility assessment	X					
Medical History	X					
Concomitant Medications	X					
Randomization	X					
Dietary counseling	X				1	
Kansas City Cardiomyopathy Questionnaire	X					
Physical Exam (including orthostatic vital signs and anthropometric measurements)	X					
12-lead ECG	X					
Laboratory tests (CBC, chem 7, methemoglobin, pregnancy test as needed)	X					
RNA collection with PAXgene tubes						
G6PD test as needed	Х					
Cognitive assessment	x					
6 minute walk test with O2 saturation	x		х			
Blood, urine and saliva collection and freezing	x		x			x x
2D echocardiogram	x	x	X X		x	х
Arterial tonometry	X		X			x x
Pill count			X X			x
Drug accountability			х			x x
Maximal effort exercise test with expired gas			X			x
Exercise cardiac output measurements			X X			x
Plantar flexor exercise / MRI			X X			X X
Assessment of Adverse events			X X			X X
Placement of Aurora device and Actigraph	X		XX		-	X X
		Х	х		XX	X

Note: For subjects participating in the ancillary study, a cardiac MRI will be performed 4-6 weeks after drug initiation in each treatment phase, on a different day than the other study procedures.

16. APPENDIX 2. ANTICIPATED STUDY TIMELINE AND KEY DATES

	2015	2016	2017	2018	2019	2020
Creation of Case Report Forms						
Creation of Database						
Site activation, Penn						
Site activation, Northwestern						
Creation of Manual of Procedures						
Initial DSMB Meeting						
Kick off meeting						
Active randomization, Penn						
Active randomization, Northwestern						
Active follow-up						
Database Lock						
Design manuscript submission						
Primary Manuscript Preparation and submission						
Ancillary Manuscripts based on unblinded data						
Ancillary manuscripts and abstracts based on blinded measures						

KEY DATES

Date of 1st patient randomized	July-Aug, 2016			
Date of last patient randomized	September 1st, 2019			
Date of last patient follow-up visit	December 7th, 2019			
Date of data cleaned and ready for analysis	April 1st, 2020			
Final manuscript preparation	April-June 2020			
Projected date of publication	October 1st, 2020			
Patients randomized per year of the study				
	Penn	Northwestern	Cumulative	Minimal Enrollment
			Total	Target
Year 1	6	3	9	7
Year 2	16	12	37	28
Year 3	12	8	57	43
Year 4	12	7	76	57
Year 5	0	0	76*	76*
		20	70	76
Total	46	30	76	/0

17. APPENDIX 3 Instructions for wearing the Aurora Device (Pulse Watch)

The Aurora device is designed to record your pulse throughout the day. We ask that you wear throughout the day and night, as you may wear a watch. During your first study visit, we will do a demonstration to teach you how to place and secure the device to your wrist.

Use of the Aurora Device is very safe. However, there are a few precautions of which you should be aware:

The wrist strap will need to be moderately tight for acquisition of good quality pulse signals. It should never be so tight, however, as to restrict circulation in the hand. If you feel a tingling sensation in the hand or wrist where the Aurora device is being worn,

immediately loosen the wrist strap. If the sensation persists, take the device off and discontinue use.

- The device will beep several times during the day. When you hear the beep, you should touch the two contacts on the front of the device with two fingers from the hand that is not wearing the device, as illustrated in the following image:

- The device has been engineered to be robust to normal daily wear conditions, but it is not waterproof. Therefore, avoid submerging the device in water or using it outdoors in heavy rain.
- The Aurora Device can be cleaned using standard isopropyl alcohol wipes. Do not use any other cleaning agents. Do not submerge the device in cleaning agents.
- Do not attempt to open the housing of the device or to dismantle the device.

